### Design and Procedures

This blinded, sham-controlled trial will feature a mixed model cross-over design, with rTMS Type (active, sham), Difficulty Level, Stimulation Location (DLPFC, PC), and Group (Young, Older adults) as factors. As such, this design reflects the fact that all subjects receive both active and sham rTMS applied to up to two different scalp locations during a WM task at up to three levels of difficulty. Study procedures are listed in **Table 1**. Up to thirty healthy young adults (age range: 18-35 years), thirty healthy older adults (age range: 55-80 years), will participate. In the initial session, which will take about 3 hours, participants will be consented and screened for the study, have a saliva sample taken, have TMS motor threshold determined, and then learn and practice the WM task. A structural and functional MRI will then be acquired within the screening visit or in a separate visit dependent on the participant's schedule. Cortical locations within PC and PFC to be used as targets for rTMS will be chosen from an analysis of subject-specific fMRI activations. Following the MRI, participants will take part in up to 5 sessions of rTMS (4 visits in Aim 1 and Aim 1b; and two visits in Aim 1c), each lasting up to 3 hours. TMS sessions will begin ~1 week after the MRI Session, to allow for time to process the imaging data, and within a 3-month period (Mondays thru Fridays), aiming to occur at the same time each day (+/- 2-3 hours for scheduling flexibility). Up to 5 rTMS sessions (involving active or sham rTMS and DLPFC (Aim 1a, Aim 1c), or PC targets (Aim 1b, Aim 1c) will use coil locations and rTMS device intensities based on realistic head modeling. Participants will report number of hours slept the previous night at each visit.

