### Subject Screening

Normal right-handed volunteers will be recruited from the community. At the beginning of their first visit to the rTMS laboratory, they will undergo neuropsychological screening (such the MINI, NACC, PHQ-9, CDR and/or BDI) and a urine test. If they pass the screening procedure, they will proceed to the rTMS lab, where

they will learn and practice the memory tasks used in the study (about 2 hrs), and will have a short session of rTMS (about 0.5 hr), in order to acclimate them to rTMS and to obtain right and left hand motor thresholds for future dosing of rTMS.

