#### **MRI/fMRI PROCEDURE:**

At BIAC, after obtaining a structural MRI and DTI and resting-state fMRI scans, fMRI data will be recorded from subjects while they perform the WM task. BOLD images will be acquired with a 3.0T GE MR Scanner. Stimuli will be back-projected onto a screen located at the head of the MRI bed using an LCD projector. Subjects will view the screen via a mirror system located in the head coil. Task onset will be electronically synchronized with the MRI acquisition computer. Task administration and collection of RT and accuracy data will be computer controlled. The scanning session will take about 1.5 hr.

Studies will be using a GE Premier Performance 3T MRI scanner, which is an improved version of GE's FDA-approved Premier system, but with better capabilities for high-resolution imaging. All operational parameters on this improved system will be within FDA guidelines to meet the same minimal risk device criteria and ensure safety of human subjects. As such, an Investigational Device Exemption (IDE) is not necessary. The research conducted under this protocol is not to evaluate the safety and efficacy of this device.

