#### **APPLICATION OF RTMS DURING WM TASK PERFORMANCE:**

The subject will be seated comfortably in a chair, facing a computer screen positioned in front of the subject for visual stimulus presentation. Earplugs will be worn to protect hearing. The participant's head may be held steady by a frame with a chin rest and the rTMS coil holder frame. A figure eight magnetic coil will be placed on the scalp and held in place with a coil fixing system supplied by MagVenture. This will be paired with the BrainSight tracking system which provides precise fMRI-guided rTMS coil placement for basic, translational, and clinical applications of rTMS. The BrainSight program enables the coil to be placed at precise cortical targets (chosen from the subject's fMRI activations from the WM task from the MRI session) on the individual's 3-dimensionally rendered brain MRI with less than one millimeter error, and enables the research team to dynamically move the coil to account for slight head movements while the subject performs the task. Five-second trains of 5 Hz rTMS will be administered at up to 130% of the individual's MT with the stimulating coil tangential to the scalp. Sham rTMS will be administered with a sham coil equipped with shielding to block magnetic field output but retain the auditory and some of the tactile aspects of active stimulation. rTMS administration will be controlled by an external computer and will be time-locked relative to stimulus presentation. A brief rTMS side effect rating scale and visual analog mood ratings will be administered before and after each rTMS block. There will be up to 12 blocks of trials per session, and each session will take about 2 hrs. Subjects' side-effects will be monitored closely. As indicated in the procedures section, side effects are assessed in a charted, structured interview both prior to and after the rTMS session. Subjects are instructed during the consent process and during the rTMS sessions about all known side effects. They are further instructed during consenting and additionally at the conclusion of the rTMS session to contact the principal investigator or study physician with any questions or concerns (including those that may arise after the experimental session has ended).

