**Imaging acquisition and preprocessing.** Three forms of structural images will be acquired: **1) full-brain high-resolution T1-weighted structural images** (inversion recovery prepared 3D SPGR) with full coverage of the head and neck, (TR = 500ms; TE = 20ms; FoV = 24cm^2; image matrix = 256x256; voxel size = 0.94 x 0.94 x 1mm), and **2) echo-planar (EPI) sensitivity encoding (SENSE) DWI images** with the same orientation (TR = 2000 ms; FoV = 24 cm^2; image matrix = 128; voxel size 0.94 x 0.94 x 1 mm; b-value = 1000 s/mm^2; 1 repetition; 36 diffusion-sensitizing directions). In addition, two forms of functional images will be collected: **1) for resting state EPI** functional imaging data, which will be used to estimate RSFA, we will acquire 24 slices parallel to the AC-PC plane using a BOLD-sensitive gradient-echo sequence with EPI k-space sampling, at TR of 2s (TE: 35ms; FOV: 25.6cm; voxel size: 63mm), and **2) event-related EPI**, which uses the same scan parameters and will measure the global reactivity to our Working Memory Task.

**TMS methods.** Coil targeting will be achieved using frameless stereotaxy (BrainSight: Rogue Research, Montreal). TMS is applied with a figure 8 coil based on 100% resting motor threshold (rMT), though TMS intensity will also be informed by E-field modeling (described below). TMS will be delivered consecutively over the individualized target region, based on the cortical site with the highest computed controllability (Network target) or parametric activity (Activity target), using a MagVenture stimulator. Neuronavigation (BrainSight, Rogue Research, Canada) and a robot (SmartMove, ANT, Netherlands) will be used to optimize the targeting. Brain atrophy could also reduce TMS effectiveness because it increases the distance between scalp and the cortex but this potential confound is addressed by adjusting TMS intensity using the E-field computation. In visits 3 to 6, participants will perform the Working Memory Task while active or electrical sham stimulation is delivered using an A/P Cool-B65 coil (MagVenture, Denmark). In a stimulation trial, twenty-five pulses of 5Hz

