Using TMS to Increase Executive Function in Older Adults

NCT02767323

Statistical Plan

Date of Approval:

01/19/2021

Data Analysis & Statistical Considerations

fMRI data:

All image pre-processing will be implemented using the FSL program (<https://fsl.fmrib.ox.ac.uk/fsl/fslwiki>). Event-related fMRI data will be extracted by time-series modeling using rectangular time windows for the memory encoding and probe phases of the task, one modeling a brief (400 ms) neural response at the beginning of the task phase, and another modeling a neural response lasting for the entire 3000 ms phase. A single rectangular function of 7000 ms will be used for the retention phase. Group data will then be analyzed using ordinal trends model (OrT: a newly-developed multivariate covariance analysis). Any fMRI network related to performance in the WM task from previous fMRI research using the WM task in young and elderly subjects will be prospectively applied to the fMRI data of the subjects. Specifically, the imaging data from the pre- and post-MRI sessions will be log transformed and subtracted from each other at each site in each subject. The global mean across sites will be subtracted from each log-transformed regional value, producing regional values normalized to each subject's global mean activity. In a second normalization, the mean for each site across subjects will be subtracted from each regional value. The result of these two normalizations is a subject x region matrix with the mean activity within and across subjects removed. This will be cross-correlated with the patterns previously found in order to quantify pattern expression for individual subjects in the present group. These individual subject pattern expressions will be entered into regressions predicting WM performance in order to verify that the patterns predict performance in new group. In addition, pattern expression will be used to predict rTMS effects on WM performance (for example, differences in RT with active and sham rTMS).

TMS data:

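### The SAP scores fMRI pattern expression from a pre/post MRI difference, but the protocol describes only one MRI per participant, before the experimental rTMS sessions

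*SAP*

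**What the plan says.** The SAP's fMRI section says that "the imaging data from the pre- and post-MRI sessions will be log transformed and subtracted from each other at each site in each subject". Each value is then centred on the subject's global mean and on the site mean across subjects. The resulting matrix is cross-correlated with patterns from earlier research to give one expression score per subject. The scores have two uses: they enter regressions predicting working memory performance, and "pattern expression will be used to predict rTMS effects on WM performance", for example the active-minus-sham difference in reaction time.

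The protocol, under Design and Procedures, says: "A structural and functional MRI will then be acquired within the screening visit or in a separate visit". It continues: "Following the MRI, participants will take part in up to 5 sessions of rTMS", with the first session about one week after the MRI. The MRI/fMRI Procedure section says: "The scanning session will take about 1.5 hr". The section on applying rTMS during the task takes coil targets from the subject's "fMRI activations from the WM task from the MRI session".

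**The concern.** The SAP's rule takes a difference between two imaging sessions in every subject, and the protocol appears to supply only one. If so, the first step of the pattern-expression analysis has no input, and everything computed from it is undefined.

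Two planned results depend on it: the check that earlier patterns predict performance in this sample, and the prediction of who benefits from rTMS. An analyst holding one scan would have to invent a substitute, choosing the task phase, difficulty contrast and scaling, possibly after seeing the behavioural results. That is avoidable analytic freedom in an analysis meant to be prospective.

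**Working it through.** The plan states no figure to reproduce here. The check is a count of scans and visits, followed by a test of the other possible readings.

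**Scans**

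| Item | Source | MRI sessions per subject |
|---|---|---|
| Needed for the subtraction | SAP, fMRI data | 2 |
| Acquired at screening or at a separate visit | Protocol, Design and Procedures | 1 |
| Described after rTMS | Either document | 0 |

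Shortfall: 2 − 1 = 1 session per subject. The MRI/fMRI Procedure section and the rTMS application section both refer to a single session, which agrees with the count of one.

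**Visits (supporting evidence only)**

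The protocol's TMS methods paragraph says: "In visits 3 to 6, participants will perform the Working Memory Task while active or electrical sham stimulation is delivered". The SAP uses the same four visit numbers for Aim 1a. One screening visit + one MRI visit + four rTMS visits = 6, so the numbering fits one MRI placed before rTMS. The highest visit number in either document is 6, and it is an rTMS visit.

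**Other readings**

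1. *Table 1 marks fMRI twice, as (X) at screening and X at the MRI session.* Design and Procedures makes these alternatives. Both also come before the experimental rTMS, so neither could be a post-rTMS scan. Table 1 is not exhaustive (the saliva sample and urine test are absent from it), so the argument does not rest on it.
2. *The rTMS given at screening makes the later MRI a post scan.* Under Subject Screening, participants "will have a short session of rTMS (about 0.5 hr") for acclimation and motor threshold. No scan is described before that session, so there is still no pair.
3. *Pre and post refer to something other than rTMS.* The SAP does not say what they are relative to. Any reading still subtracts one session from another.
4. *One document supersedes the other.* Both carry the same approval date, 01/19/2021.

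**What depends on the difference**

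The chain is: log difference → two centrings → subject-by-region matrix → expression score → prediction of performance and prediction of rTMS effect. With one scan the first step fails, and so does each later one. First-level time-series modelling, target selection and the Aim 1a, 1b and 1c ANOVAs are outside this chain.

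**A related sign**

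The SAP models retention at 7000 ms and the probe at 3000 ms; the protocol's WM Tasks section gives 5 seconds and 4 seconds. This suggests, without proving it, that the SAP's fMRI text was not aligned with the current task design.

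**The case against.** No second MRI can be found in either document, so the other side can dispute only the supporting evidence, the size, the remedy and the weight.

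- **Visit numbering.** The SAP gives visits 3 to 6 for Aim 1a only. The protocol gives Aim 1c two rTMS visits and elsewhere allows up to five, so the numbering is not a full account of visits. This stands: the numbering only corroborates. The sections describing the single MRI carry the point without it.
- **Number of regressions.** The SAP says regressions, with no count, for performance, and names no method for predicting the rTMS effect. This stands as a matter of wording: the documents support two predictive uses, not exactly two models.
- **Participant count.** Figure 1 lists 29 + 18 + 15 + 15 + 14 = 91 participant entries, and none has a second MRI described. Overlap between cohorts is not stated, and the protocol plans up to 30 + 30 = 60 people, so 91 should not be read as people affected. This stands.
- **Change score.** If both scans exist, the difference can be computed, and its association with the rTMS effect is a legitimate question. It is, however, a different question. Every subject receives active and sham, so a scan after the rTMS sessions follows the stimulation whose effect is to be predicted. A change containing that scan is not a pre-treatment predictor.
- **Weight.** The analysis is supporting, and the objective and endpoint shown in the protocol concern working memory performance. That limits the severity, but a named analysis that cannot be run as written still needs correcting.

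**Conclusion.** The concern holds. The SAP's rule needs two MRI sessions per subject and the protocol describes one, before the experimental rTMS sessions. The pattern-expression score and both of its predictive uses are therefore undefined as written.

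The damage is confined to this supporting imaging analysis; the primary active-versus-sham comparison stands without it. The conclusion assumes that the protocol's description of MRI sessions is complete. The documents do not show whether the SAP is wrong or the protocol omits a scan. The point should be fixed, and confidence in the contradiction is high.

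**What to change.** Establish which document is right, then make the matching change.

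- **One MRI is done.** Replace the pre/post subtraction with pattern expression computed from the single task fMRI acquired before the experimental rTMS sessions. Name the estimate or contrast used (task phase or difficulty level) and keep the two mean-centrings. State a scaling that suits this input and is consistent with how the earlier patterns were derived; a log transform cannot be applied to contrast values that are zero or negative. State that this baseline score is the predictor in both analyses. Cost: SAP wording only.
- **A post-rTMS MRI is done.** Add it to the protocol text and Table 1 with its timing, and say in the SAP what pre and post refer to. Still use the pre-rTMS scan to predict the rTMS effect; any analysis of change should be listed separately as its own question. Cost: a schedule entry plus SAP wording.
- **A second MRI was intended but not acquired.** Wording cannot restore the planned difference. Say so, and use the single-scan score as in the first case.

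In every case, settle the definition before the scores are related to performance or to the rTMS effect, and bring the SAP's phase durations into line with the protocol in the same edit.

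### The fMRI pattern-expression regressions name no Group term, so in a mixed-age sample age gaps in both variables can mimic or mask a brain-behaviour association

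*SAP*

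**What the plan says.** The SAP, under fMRI data, takes patterns from earlier work, "Any fMRI network related to performance in the WM task from previous fMRI research using the WM task in young and elderly subjects", and scores each new subject on them. The input is a within-subject change: "the imaging data from the pre- and post-MRI sessions will be log transformed and subtracted from each other at each site in each subject". Each subject's global mean is then removed, and after that "the mean for each site across subjects will be subtracted from each regional value". The resulting scores have two uses:

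- **Performance.** "These individual subject pattern expressions will be entered into regressions predicting WM performance", with the stated purpose "in order to verify that the patterns predict performance in new group".
- **rTMS response.** "pattern expression will be used to predict rTMS effects on WM performance", with the active-sham difference in RT as the example.

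Neither regression is given a Group or age term, an interaction, or separate fits by age. The fMRI section is not divided by aim. The TMS data section is, and there Group is a between-subject factor in the Aim 1a ANOVAs.

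The trial enrols two well-separated age groups (Protocol, Design and Procedures): "Up to thirty healthy young adults (age range: 18-35 years), thirty healthy older adults (age range: 55-80 years), will participate". In Figure 1 of the Protocol only Aim 1a has both ages (29 young, 18 older). Aim 1b has 15 older adults; Aim 1c has 15 and 14 young adults in its two cohorts.

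**The concern.** If young and older adults enter one regression without Group, the slope mixes two things: the association among people of similar age, and the line joining the two group means. When the groups differ on both variables, the second part alone can make the slope significant, or can cancel a real within-group slope.

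The Protocol's opening rationale makes gaps on both sides plausible. It describes decline in working memory with age, expects older adults to lean more on prefrontal cortex, and predicts a larger DLPFC benefit for them. The last expectation bears on the second regression: if it is right, and expression also differs by age, the pattern would seem to predict rTMS response even if it says nothing about who responds within an age group. The earlier patterns came from both ages, so they may carry an age contrast themselves.

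At stake is the mechanistic claim that a known network predicts performance and rTMS response in new subjects. The active-sham ANOVAs are not touched.

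**Working it through.** The plan gives no effect size, power or alpha for these regressions, so there is no stated figure to reproduce.

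**Inputs from the documents.** Aim 1a: 29 young + 18 older = 47 (Protocol, Figure 1). Enrolment ceiling: 30 + 30 (Design and Procedures). All Figure 1 cohorts together: 29 + 15 + 14 = 58 young and 18 + 15 = 33 older. These totals exceed 30 per group unless some people served in more than one cohort, so this case is only an upper scenario.

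**Assumptions.** Two-sided 0.05; no association within either age group; age gaps of dx SD in expression and dy SD in the outcome, ranged because the documents give no sizes.

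**Implied pooled correlation.** With p the share of older adults,

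|rho| = p(1-p)·dx·dy / sqrt{[1 + p(1-p)dx²][1 + p(1-p)dy²]}

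For equal gaps d this is p(1-p)d² / [1 + p(1-p)d²]. In Aim 1a, p = 18/47 = 0.383 and p(1-p) = 0.236:

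- d = 0.5: 0.059/1.059 = 0.06
- d = 0.8: 0.151/1.151 = 0.13
- d = 1.0: 0.236/1.236 = 0.19
- d = 1.5: 0.532/1.532 = 0.35

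**False-positive rate.** Simulation, 10,000 runs per setting, slope test by ordinary least squares:

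| Gap in both (SD) | 29+18, no Group | 29+18, with Group | 30+30, no Group | 58+33, no Group |
|---|---|---|---|---|
| 0.3 | 5.2% | 4.8% | 5.4% | 5.6% |
| 0.5 | 6.8% | 5.0% | 7.4% | 7.6% |
| 0.8 | 14.4% | 5.2% | 18.4% | 23.0% |
| 1.0 | 25.8% | 5.1% | 34.8% | 43.4% |
| 1.2 | 43.4% | 5.3% | 56.2% | 68.5% |
| 1.5 | 71.2% | 4.8% | 85.6% | 93.6% |

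**One gap only (29+18, no Group).** With 1.0 SD in the outcome and none in expression the rate is 5.1%; with 1.0 SD in expression and none in the outcome it is 5.0%. Both gaps are needed.

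**Role of the centring.** A 60-region simulation (29+18, 3,000 runs) applied the SAP's two normalisations and correlated the result with a prior pattern. Without Group, the rates at 0.5, 0.8 and 1.0 SD were 6.0%, 12.5% and 26.4%. Weighted-sum scores with no site-mean removal gave 6.3%, 12.9% and 26.6%. Removing one common site mean shifts every weighted-sum score by the same constant, so it cannot change that slope. Adjusting the correlation scores for Group brought the rates to 4.5%, 4.6% and 5.2%.

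**Masking and cost (29+18, within-group r = 0.4).** With no age gaps, power is 81% without Group and 80% with it. With 0.8 SD gaps running against the true slope, power is 29% without Group and 80% with it.

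**The case against.** **Pooling is inferred.** The SAP never says outright that the ages are combined or that expression is the sole predictor; it leaves the model unspecified. This stands as a limit on the point. A reader might infer that the plan prescribes a pooled, single-predictor model, but it does not. Pooling is the literal reading of a section that speaks of all subjects and names no other term, and that is enough to ask for the term.

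**The centring is not the cause.** A reader might blame the removal of site means over all subjects. It merely fails to take the age gap out; the missing Group term does the damage.

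**The gaps may be small.** Expression is built on a pre-post difference, so an age difference that is stable across sessions cancels and only an age difference in change survives. Task difficulty is set for each person from screening performance (Protocol, WM TASKS), which may narrow the performance gap. Both are fair. However, Table 1 of the Protocol lists a single MRI session and none after rTMS, so the subtraction may not be available, and nothing says that individual set sizes equate RT.

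**The rTMS outcome is a within-subject difference.** Baseline age differences in RT largely cancel from it, so confounding there needs an age gap in the rTMS effect itself. That is correct, and the Protocol hypothesises such a gap for DLPFC without giving its size.

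**Between-age variation may be of interest.** A trial about compensation in ageing could want it. That is a choice of target which the SAP should state. A pooled slope cannot separate the two sources, whereas a model with Group reports each.

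**Conclusion.** The point holds for any regression that contains both ages: Aim 1a, or any pooling of cohorts. It does not apply to Aims 1b and 1c analysed alone.

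The size depends on gaps that the documents do not give. For 29 + 18, inflation is slight up to about 0.5 SD in both variables, material from about 0.8 SD and severe by 1.5 SD; a real association can equally be masked. A reader might infer that an age difference alone is enough to verify the pattern. It is not: with a gap in only one variable the error rate stays near 5%. Nor do the documents show that confounding will occur, only that the analysis as written has no protection against it.

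This is a supporting imaging analysis, so the consequence is a possible wrong mechanistic conclusion rather than a wrong primary result. The change is still worth making, because Group is already recorded and adjusting for it costs almost no power.

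**What to change.** In the fMRI data section of the SAP:

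1. State for each regression which cohorts enter and whether the ages are analysed together or apart.
2. Wherever both ages enter, add Group and Group x pattern expression, for the WM-performance outcome and for the active-sham outcome.
3. Base verification on the within-group slope. Say how it is read when the interaction is in the model (a slope for each age group, or their average with Group coded symmetrically), since under 0/1 coding the expression coefficient is the slope in the reference group only.
4. Leave the centring as it is. Centring within Group without a Group term also controls the error, but is conservative: 3.0% at 1.0 SD and 1.3% at 1.5 SD for 29 + 18.
5. Reconcile the pre-post subtraction with Table 1 of the Protocol, which shows no MRI after rTMS, because it decides how much of an age gap can remain in the scores.

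The cost is one SAP line for the model terms and one or two degrees of freedom; no new data are needed. The power figures of 80% and 81% are for adding Group alone; the model with the interaction was not simulated.
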